8.2 Video calls

Participants will receive a tablet for the duration of the intervention for video conferencing with research team. Phone call conferencing will be available, however the tablets allow for video applications so that participants can visually interface with members of the research team. Additionally, using video conferencing allows participants to receive feedback and form recommendations from her home if she has questions or would like feedback on her performance for specific exercises. However, because this is a pilot intervention, we aim to determine if the video

conferencing component is useful. By providing each participant with a tablet, we are inclusive for individuals who may not have access to these resources on her own. Each participant will receive a check-in at eight points during the 10 week study: two calls in the first week, one during weeks three four and five, one during week six , and finally one during week eight consistent with their preferred contact method to provide feedback on their progress and resistance training. The study coordinator will ask about overall qualitative satisfaction, and issues the participant is having, and any questions that the study coordinator could potentially address. Participants are welcome to reach out to the lab or study coordinator at any point during the study, however these pre-planned check in visits will hopefully facilitate discussion if any issues remain unaddressed.

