4.1 General Design

- A phase III, randomized, two-arm trial with a wait-list control group
- The intervention itself is 10 weeks, with an additional five week follow up assessment for those in the exercise arm to determine adoption of the program. Overall, the anticipated total duration should be 20 weeks for participants
- The intervention will consist of (a) an initial in-person instructional session; (b) instructional materials and resistance training equipment (e.g., resistance bands) and (c) support and feedback provided via video coaching sessions; and (d) a final in-person study visit to collect post-study measures for both groups

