7.7.2 Data Collection and Follow-up for Withdrawn Subjects

Data will be attempted to be gathered from participants who have withdrawn from the study to collect their data prior to their withdrawal, including emails from the research staff and telephone calls.

Withdrawn subjects will be analyzed using an intent to treat analysis, therefore maximizing the amount of data is paramount to success. However, if participants cannot be contacted after 3 attempts from the study team (both telephone calls and emails) then the participants will be considered lost to follow-up.

8 Study Procedures

Wait list interventions

After being randomized to the wait-list group, participants will be scheduled for their 10 week follow up visit. The wait list arm will not have the additional five week follow up that the exercise arm receives. Participants will be reminded that at that final visit, participants will complete the same study measures (body composition, functional fitness testing, blood sample collection, and anthropometrics) and will also receive study materials at the end of their wait list period. Participants in the wait list group will also complete accelerometer (Actigraph) assessments at three study points: Early in the intervention near the instructional visit, at the mid-way (5-week) mark, and before the final visit. These accelerometers will be sent and received via mail and participants will receive instructions on how to wear, use and send to us during the instructional visit.

Exercise interventions

After being randomized to the exercise (intervention) arm, participants will be scheduled for an instructional visit with the study coordinator within a week of randomization. At that visit, participants will be instructed to wear comfortable clothes and shoes for learning the exercises. The instructional visit includes going through each exercise of the intervention (see Table below) to learn the movement, learn the muscle groups involved, and to learn how to monitor themselves by tracking their progress via logs. This instructional visit should take 60-90 minutes, and each participant will receive a summary sheet of her starting point at each exercise with respect to intensity and progressions/regressions. For example, a participant may be starting on a blue resistance band for biceps curls, but the squats may simply be body weight at this time. Table below outlines the exercises for the intervention.

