Table 2. Series of exercises, with progressions and regressions to increase/decrease difficulty.

Primary muscle group	Exercise	Progressions	Regressions
Thighs (quadriceps, hamstrings)	Body weight squats	
• Add resistance band• Holding dumbbells	
• Chair squats• Shortened range of motion
Calves (gastrocnemius, soleus)	Standing heel raises	
• Holding dumbbells• Elevate ball of foot	
• Shortened range of motion
Chest (pectoralis major & minor)	Standing chest press	
• Increase band tension	
• Reduce band tension
Back (trapezius, latissimus dorsi)	Seated banded row	
• Standing row• Increase band tension	
• Reduce band tension• Shorten range of motion
Abdominals (rectus & transversus abdominus)	Static v-sit hold with feet on floor	
• Elevate feet• Add rotation• Add dumbbell	
• Support with hands• Add lumbar support w/ towel
Shoulders (deltoids)	Seated banded press	
• Standing• Use dumbbells	
• Reduce band tension• Shorten range of motion
Biceps brachii	Seated banded curl	
• Standing• Add tension to band• Use dumbbells	
• Reduce band tension• Shorten range of motion
Triceps brachii	Seated arm extension	
• Increase band tension	
• Reduce band tension

During the study period, participants in the intervention arm will be instructed to complete the exercise routine twice a week for 10 weeks during the intervention, and also continued throughout the five week follow up period. There are eight video calls with the study coordinator to check in, to identify any issues or concerns with the exercises, and to finally monitor progress in the form of assessing volume/intensity/difficulty of each of the exercises. These calls are done over video so that the coordinator can build rapport with participants, and that participants can show

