10.4 Data and Safety Monitoring

The Site Investigator ([name]) will be responsible for reviewing and monitoring all study data and any adverse events for this study. The Investigator will meet with study personnel at least weekly to evaluate study progress, including periodic assessment of data quality and timeliness, participant recruitment, accrual and retention, participant risk versus benefit, and other factors that can affect study outcomes. All unanticipated problems regardless of where they occur, will be reported to the University of Wisconsin IRB.

This protocol is considered to have a minimal risk to participants, as it prescribes physical activity that is consistent with national recommendations and guidelines for cancer survivors. We attempt to reduce the risk of injury or muscular soreness by excluding individuals who report difficulty transitioning from sitting to standing, walking 1 block (as a proxy measure of basic physical functioning), or report that they are otherwise unable to work towards the intervention goals. As with any exercise intervention, there is also a minor risk of cardiovascular events. Participants in both intervention groups will receive regular check-in calls to assess progress and address any potential problems regarding physical issues or emotional stress.

11 Assessment of Safety

This protocol is considered to have a minimal risk to participants, as it prescribes physical activity that is consistent with national recommendations and guidelines for cancer survivors. We attempt to reduce the risk of injury or muscular soreness by excluding individuals who report difficulty transitioning from sitting to standing, walking 1 block (as a proxy measure of basic physical functioning), or report that they are otherwise unable to work towards the intervention goals. As with any exercise intervention, there is also a minor risk of cardiovascular events. Participants in both intervention groups will receive regular check-in calls to assess progress and address any potential problems regarding physical issues or emotional stress.

12 Study Finances

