Appendix 1: Participant tracking form: Checklist of Study Activities

Activity	Date completed	Staff initials
Screening call	/ /	_____
Baseline Assessments (all participants)		
Confirmation Letter sent	/ /	_____
Demographics and cancer characteristics	/ /	_____
Physical Measures (FFT and Anthropometrics)	/ /	_____
DXA Scan	/ /	_____
Blood biomarkers collected	/ /	_____
Questionnaire links emailed (5 questionnaires)	/ /	_____
Actigraph/instructions given	/ /	_____
Randomized to:  Intervention  Wait-list	/ /	_____
If intervention: Instructional visit scheduled	/ /	_____
Baseline Questionnaires verified	/ /	_____
Baseline incentive provided	/ /	_____
Instructional Visit (Intervention group)		
Date of visit – all exercises taught	/ /	_____
Participant exercise materials delivered	/ /	_____
ActiGraph data downloaded/checked	/ /	_____
Intervention materials provided (Both groups)	/ /	_____
Intervention Period (Intervention group)		
Date of first coaching call (1A)	/ /	_____
Date of second coaching call (1B)	/ /	_____
Date of week 2 coaching call (2)	/ /	_____
Date of week 3 coaching call (3)	/ /	_____
Date of week 4 coaching call (4)	/ /	_____
Actigraph mailed out	/ /	_____
Mid-point (5 week) Questionnaires Sent (5)	/ /	_____
Mid-point Questionnaires Verified	/ /	_____
Date of week 6 coaching call (6)	/ /	_____
Date of week 8 coaching call (8)	/ /	_____
Actigraph data downloaded/checked	/ /	_____

Final Assessments (all participants)

Final visit scheduled	/	/	
ActiGraph mailed	/	/	
Questionnaire links emailed (5 questionnaires)	/	/	
Questionnaires verified	/	/	
Physical Measures (FFT and Anthropometrics)	/	/	
DXA Scan	/	/	
Blood biomarkers collected	/	/	
Accelerometer downloaded/checked	/	/	
Incentive delivered	/	/	
Qualitative interview with study coordinator	/	/	

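### The check-in calls are listed inconsistently and promised to different arms, and unequal contact may by itself shift the between-arm description of adverse events

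*Combined protocol and SAP*

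**What the plan says.** **Number of calls.** Section 8 (Exercise interventions) says "There are eight video calls with the study coordinator to check in". Section 8.2 repeats the number and itemises it: "check-in at eight points during the 10 week study: two calls in the first week, one during weeks three four and five", followed by one call in week 6 and one in week 8. Appendix 1 has call lines for 1A, 1B and weeks 2, 3, 4, 6 and 8. One of them, "Date of week 2 coaching call (2"), has no counterpart in section 8.2. For week 5, Appendix 1 has only "Mid-point (5 week) Questionnaires Sent (5").

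**Who is called.** Section 4.1 lists "support and feedback provided via video coaching sessions" as a component of the intervention. Appendix 1 puts the call lines under "Intervention Period (Intervention group"). For the other arm, section 8 (Wait list interventions) says "After being randomized to the wait-list group, participants will be scheduled for their 10 week follow up visit"; it adds accelerometers sent by mail and mentions no calls. Against this, one sentence printed in both section 10.4 and section 11 reads: "Participants in both intervention groups will receive regular check-in calls to assess progress".

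**Safety.** Section 4.1.3 makes the total count of adverse events during the intervention the primary safety endpoint. Section 9.3.1 has those counts described between groups. Table 3 ticks Safety at 4-6, 10 and 15 weeks without naming an arm. Neither section 8.1 nor section 8.2 sets out safety questions to be asked.

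**The concern.** Two things are at stake.

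The first is what is delivered. Staff working from section 8.2 would call in week 5 and not in week 2. Staff working from the Appendix 1 checklist would do the reverse. In a pilot meant to field-test the components of an intervention, the dose of coaching should be unambiguous, and the coaching call completion figure collected under Table 3 needs one denominator.

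The second is how adverse events come to be known. In section 8.2 the coordinator asks on each call whether the woman is having problems. The exercise arm also has an instructional visit and session logs with a line for concerns (Appendix 3). If the wait-list arm is not called, its women have far fewer occasions to mention a complaint. Soreness and similar mild events may surface mainly when someone is in touch. A higher count in the exercise arm could then reflect more contact, more harm or both, and the planned description could not separate them.

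**Working it through.** **Step 1: the stated number.** Sections 8 and 8.2 both give 8 calls.

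**Step 2: count the lists.**

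- Section 8.2: 2 (week 1) + 3 (weeks 3, 4, 5) + 1 (week 6) + 1 (week 8) = 7. If the phrase about weeks three to five means a single call, the count is 2 + 1 + 1 + 1 = 5. Neither gives 8.
- Appendix 1 call lines: 1A, 1B, 2, 3, 4, 6, 8 = 7. The week-5 row would make 8 contact points if it were counted.
- Calls on both lists: 1A, 1B, 3, 4, 6, 8 = 6. Week 5 is only in section 8.2; week 2 is only in Appendix 1.
- The lists merged: 1A, 1B, 2, 3, 4, 5, 6, 8 = 8.

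The merged list matches the stated number, so it is probably what was intended, but no section states it.

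**Step 3: the week-5 row.** Section 8 describes the mid-point questionnaires as sent by email, which is not a call. The 5 in brackets could be a week label like those on the call lines. It could also mean five questionnaires, since the baseline and final rows of the same form give that number. The text does not settle it.

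**Step 4: effect on call completion.** A woman who receives every call on either list scores 7/8 = 87.5% against the stated number, or 7/7 = 100% against the list. With 40/2 = 20 women per arm, that is 20 × 7 = 140 calls listed against 20 × 8 = 160 stated.

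**Step 5: scheduled contacts from randomization to the week-10 visit.** The Table 3 mid-point safety check is counted once in each arm, separately from any week-5 call. The allocation phone call (section 8.5) goes to both arms and is left out.

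| Reading | Exercise arm | Wait-list arm |
|---|---|---|
| Calls to exercise arm only | 7 or 8 calls + instructional visit + mid-point check + final visit = 10 or 11 | mid-point check + final visit = 2 |
| Same calls to both arms (10.4 and 11 taken literally) | 10 or 11 | 7 or 8 calls + 2 = 9 or 10 |
| Calls to exercise arm only, and no mid-point check in either arm | 9 or 10 | 1 |

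Adding the allocation call raises every entry by 1. The exercise arm also keeps 2 × 10 = 20 session logs per woman, but section 8.1 has them handed in at the final visit, so they are not 20 separate contacts with staff.

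**Step 6: why the contact ratio is not a reporting ratio.** The chance that an event surfaces at a given contact is not in the documents. As an illustration only, assume equal true event rates, onset uniform over 10 weeks, calls at the Appendix 1 times to the exercise arm only, safety checks at weeks 5 and 10 in both arms, and the same independent chance q of an event surfacing at each later contact. The ratio of reported events, exercise to wait-list, is then about 1.63 at q = 0.3, 1.32 at q = 0.5, 1.14 at q = 0.7 and 1.03 at q = 0.9. The range runs from material to negligible, and nothing in the plan places this trial within it.

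**The case against.** The strongest reply is that little depends on the call count. Coaching call completion is listed in Table 3 as additional data; it is not an endpoint and no analysis in section 9.3.1 uses it. Adherence is defined from the exercise logs in section 8.1 and analysed as sessions completed against sessions prescribed. This stands. A reader might infer that the seven-or-eight discrepancy disturbs the primary endpoint, because section 4.1.1 also names video sessions as a source. The documents do not support that: the calls do not enter the adherence denominator.

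It can also be said that Appendix 1 is complete if its week-5 row is a contact point, so that only section 8.2 has dropped a week. That is possible. It would remove one inconsistency but leave the one within section 8.2.

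On safety, Table 3 already ticks a check at 4-6 and 10 weeks and limits neither to one arm. Accelerometry at the mid-point is expressly stated for the wait-list arm, so a common safety check is the natural reading. This also stands, and it is why the comparison is 10 to 11 contacts against 2 and not 9 to 10 against 1. It does not dispose of the point, because no common questions are specified and the calls, the instructional visit and the logs remain on one side.

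Finally, this is a minimal-risk pilot of 40 women with a descriptive safety analysis, closer contact is expected in a coached arm, and section 8.2 lets participants contact staff at any time. All true, and each limits the severity.

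**Conclusion.** The inconsistencies are real. Eight calls are stated, section 8.2 itemises seven, and Appendix 1 has seven call lines plus an ambiguous week-5 row. The sentence in sections 10.4 and 11 cannot be reconciled with section 8 and Appendix 1. The call count affects the intervention as delivered and the completion figure (87.5% or 100% for full delivery of a list), but no endpoint.

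The more important consequence is for safety reporting. If calls go to the exercise arm only, that arm has about 10 to 11 scheduled contacts to week 10 against about 2, so the between-group description of the primary safety endpoint may differ through reporting alone. This assumes that the Table 3 mid-point check applies to both arms. If both arms were called, the imbalance would be small (10 to 11 against 9 to 10), with the instructional visit and the logs remaining.

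A reader might infer that about five times the contacts means about five times the reported events, or that the safety comparison is invalid. Neither follows. Contacts are occasions to report, not structured enquiries; the size of any difference cannot be derived from the documents; and no test or stopping rule is affected. Severity is minor to moderate.

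**What to change.** 1. Have the investigators confirm one eight-call schedule, probably 1A, 1B and weeks 2, 3, 4, 5, 6 and 8, and use it in section 8.2 and Appendix 1. Eight is then the denominator for coaching call completion. The merged schedule is an inference and needs their confirmation.
2. Correct the sentence in sections 10.4 and 11 to say that coaching calls go to the exercise arm only.
3. Ask both arms the same short safety questions at the time points Table 3 already ticks, 4-6 and 10 weeks, each covering the time since the previous check (the first since randomization). Base the between-arm description on those answers. Report events known only from calls or logs separately for the exercise arm. Keep total adverse events as the safety endpoint. For the wait-list arm, the mid-point questions can travel with the accelerometer already mailed at about 5 weeks.

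The cost is a few wording changes, one added call line in Appendix 1 if the merged schedule is confirmed, a short question set, a brief mid-point contact with about 20 wait-list women, and one extra split in the adverse event table. No additional staff should be needed. The drawbacks are a smaller count in the compared set and recall over about five weeks. Women who have been coached by phone or video may still remember and report more, so the common questions should reduce the difference but may not remove it.

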8.3 Labs

Blood spots: In a non-clinical setting, dried blood spots collected using finger pricks are a low-cost way to establish the feasibility of biomarker data collection. Using a standardized protocol, participants will undergo a fingerpick to collect a peripheral blood sample to assess glycosylated hemoglobin (A1c) and c-Reactive Protein⁵⁰ via dried blood spots. Dried blood spots can be collected by non-phlebotomists in non-clinical settings, and the values for both A1c and CRP are highly correlated between dried blood spots and venipuncture.⁵¹

8.4 Established Standard of Care:

There are currently no established standards of care in terms of prescribing exercise (especially resistance training exercise) in endometrial cancer survivors.

Table 3. Study Calendar of scheduled measures

Modifications proposed				
	Baseline	4-6 Weeks	10 Weeks	15 Weeks
Demographics	✓			
Cancer characteristics	✓			
Anthropometrics	✓		✓	
Body composition	✓		✓	
Biomarkers (blood spots)	✓		✓	
Physical activity (self-report)	✓	✓	✓	
Physical activity (device ¹)	✓	✓	✓	✓
Functional fitness	✓		✓	
Quality of life	✓	✓	✓	
Self-efficacy	✓	✓	✓	
Satisfaction & feedback	✓	✓	✓	✓
Safety		✓	✓	✓
Additional data collected during intervention:				

 • Adherence logs (weekly) • Coaching call completion 				
<small>¹We will be using accelerometers for data collection, as opposed to Fitbits in the original proposal, as accelerometers are the gold standard physical activity measure</small>				

will be scheduled for the intervention introductory session. (Those in the wait-list control group will receive this session at the same time as the final measures are collected.)

Instructional. Participants randomized to the intervention group will meet with study coordinator to learn how to conduct the exercises, how to use the materials, how to complete the exercise log and general instructions on the normal symptoms of resistance training. This visit should take 1-2 hours, ensuring the participant is confident.

8.4.2 Follow up:

8.5 Study Visits

8.4.1 Screening/Baseline:

Baseline. At this visit, the study coordinator will explain the study and obtain written informed consent. Physical measurements (anthropometrics, blood sample, DXA scan, functional fitness testing) will be completed. The study coordinator will instruct the participant on how to properly wear the accelerometer (to be returned via pre-paid mailer), complete a 7-day PA log, and complete the online questionnaires.

Randomization. After all baseline measures have been completed and checked, the participant will be randomized with 1:1 probability to the intervention or wait-list control group. A blocked randomization scheme will ensure equal allocation of participants to each group. Participants will be notified of their group assignment by phone; those in the intervention group

Table 4. Acceptable Window for Study Visits (including weekends)

Visit	Window	Activities
Randomization	+/- 5 days	Allocate to group
Instructional visit	+/- 2 weeks	Teach exercises, learn how to interface with software, how to log exercises
Final visit	+ /- 2 weeks	Collect final measures

8.4.3 Unscheduled:

- Pain or concerns that need to be addressed in person
- Adverse event follow ups with PCP

8.4.4 Final Study Visit

Final Visit. All participants will return for follow-up assessments at 10 weeks. In advance, the participant will be mailed an accelerometer and 7-day PA log and will receive a link to complete the online questionnaires. Physical measures (anthropometrics, blood sample, DXA scan, functional fitness testing) will be completed. Those women in the wait-list control group will receive their introductory intervention session at this visit.

9 Study Analysis

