9.1 Sample Size Determination

Sample Size and Power. The purpose of this trial is not to conduct hypothesis testing, but rather to field-test the intervention to identify adherence rates to exercise prescription across a group of participants. At this time, the anticipated effect size is unknown and the sample size of 40 has been selected to maximize feasibility in the anticipated time frame for this project.

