9.3 Subject Population(s) for Analysis

The populations for this investigation include:

- All-randomized population: Any subject randomized into the study, regardless of whether they received study agent
- All-treated population: Any subject randomized into the study that received at least the instructional visit of the intervention
- Protocol-compliant population: Any subject who was randomized, was allocated to the exercise group and provided at least one set of data elements required by the protocol.

9.3.1 Describe the types of analysis:

- **Primary Analysis:** The primary objective includes measuring the percentage of completed sessions compared to prescribed, and a one-sample t-test will be conducted to determine if that proportion, across participants, is >90%. A one-sample t-test will be done to determine if retention is >90%.

- **Secondary Analyses:** The secondary analyses includes measuring the objective and functional changes from pre to post intervention as well as differences between groups. Paired ANOVAs and descriptive statistics will be used to analyze functional and objective data, as well as participant feedback data, including satisfaction with each component of the intervention.
- **Exploratory, longitudinal analyses:** Content analysis will be done on the qualitative interviews to examine barriers to physical activity, as well as satisfaction with the intervention, and identification of themes to improve the intervention. Although formal hypothesis testing is not part of our specific aims, we will conduct longitudinal analyses of the data we collect to estimate potential magnitude of expected changes, as well as longitudinal analysis of the repeated measures.
- **Safety Analysis:** The safety analysis includes simple descriptive analysis about the number of adverse events over the course of the intervention between groups and across sites.

9.4 Planned Interim Analysis:

There are no planned interim analyses for this investigation.

10 Data Collection, Handling and Record Keeping

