10.3 Records Retention

To ensure the integrity of the data collected from study participants, several procedures will be implemented. All personnel involved in data collection will be thoroughly trained in all assessment methods, thus ensuring consistent applications of procedures and measurement consistency across participants. All questionnaire data will be automatically saved in the secured, password protected Qualtrics or REDCap systems and will be downloaded to a password protected network folder on a secure server (i.e., password protected) which is backed up daily ensuring access only by the investigators. All other data will be saved to a computer hard drive in real time and then stored on a secure server (i.e., password protected) which is backed up daily. All raw data are kept in locked cabinets in the site-PI's laboratory. All hardcopies of raw data will be de-identified (with the exception of the study ID number) and copied for mailing to the coordinating center for data management. Although all packages with data will be mailed by certified mail so that tracking the location is possible, maintaining copies of the data at the collaborating centers in locked cabinets in the site investigator's laboratory will be done in the unlikely event that data is lost in the mail. Informed consent forms will be kept in a separate locked file cabinet with restricted access. Issues related to data integrity will be discussed on a weekly basis as a recurring agenda item in the weekly project meeting. Finally, continuing review of all procedures will be obtained by all appropriate institutional review boards.

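### Final fitness tests are done at a visit where the arm is known, with no masking, fixed encouragement or testing-first rule described, so secondary between-group functional estimates could be biased

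*Combined protocol and SAP*

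**What the plan says.** **Timing of allocation.** Under section 8.5 (Screening/Baseline), all baseline measures are finished and checked first; then "the participant will be randomized with 1:1 probability to the intervention or wait-list control group".

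**Final visit.** Section 8.4.4 brings all participants back at 10 weeks for anthropometrics, blood sample, DXA and functional fitness testing, and adds: "Those women in the wait-list control group will receive their introductory intervention session at this visit". The text beside Table 3 likewise places that session at the time of the final measures. Section 8 (Exercise interventions) gives the exercise arm an exit interview with the coordinator at this visit. Neither 8.5 nor 8.4.4 names the person who takes the physical measures.

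**The coordinator's role.** Section 5 provides for a single main coordinator. At baseline, "the study coordinator will explain the study and obtain written informed consent". The coordinator also teaches the exercises and makes the coaching calls, of which section 8 says: "These calls are done over video so that the coordinator can build rapport with participants".

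**The tests.** Section 8.1 describes six. The chair stand, arm curl, 6-minute walk and 8-foot up-and-go ask for as many repetitions, as much distance or as much speed as the woman can manage.

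**Standardisation.** Section 8.1 gives a procedure for each test. Section 10.3 states: "All personnel involved in data collection will be thoroughly trained in all assessment methods".

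**Use of the data.** The secondary analyses in 9.3.1 cover "measuring the objective and functional changes from pre to post intervention as well as differences between groups". The exploratory analyses are to gauge how large the changes might be.

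**The concern.** A tester who knows the arm, and who may have coached one arm for ten weeks, can encourage women differently or count borderline repetitions differently. A woman tested by her coach may also try harder. None of this need be deliberate.

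The wait-list session makes the arm plain to anyone present, as does the exit interview. Appendix 1 adds a further route: one tracking form carries both the randomised arm and the final fitness tests and DXA.

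What is at stake is the credibility of the between-group functional and body-composition differences. Section 9.2 says there are no published effect sizes for this intervention in this population, so readers are likely to give these estimates some weight. A bias of this kind has a direction and, unlike sampling error, does not shrink as more women are enrolled.

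**Working it through.** The plan has no figure to reproduce. Section 9.1 says "the anticipated effect size is unknown" and that "the sample size of 40 has been selected to maximize feasibility in the anticipated time frame for this project"; no SD, power or alpha is given. The check is therefore one of logic, plus a look at whether the data could reveal a bias.

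**1. Why the bias enters only at follow-up.** Write m0 for any tester influence on the mean score at baseline, mE and mW for the influence at follow-up in the exercise and wait-list arms, cE and cW for the true mean changes, and D = cE − cW for the true difference in change. Before randomisation nobody knows the arm, so m0 has the same expectation in both arms. The expected difference in measured change is

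(cE + mE − m0) − (cW + mW − m0) = D + (mE − mW).

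The baseline term cancels. The follow-up term does not, and baseline adjustment cannot remove it because it arises after randomisation. It is zero only if the tester's influence is the same in both arms.

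**2. What the supplied text does to keep mE equal to mW.**

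| Safeguard | Supplied text |
|---|---|
| Test procedure | Described for each test (8.1) |
| Training for consistency | Promised (10.3) |
| Standard encouragement wording | Not found |
| Tester independent of coaching | Not stated; tester not named |
| Arm kept off the recording form | No; Appendix 1 shows it |
| DXA analysed with the arm withheld | Not found; data carry a study ID (10.3) |
| Testing before the wait-list session | Not stated |
| Testing before the exit interview | Appendix 1 lists the interview last, but as a checklist order, not a rule |

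The only mention of masking, in 10.1.1, concerns identifiers in copied records.

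**3. Could the data reveal it?** Inputs: 40 women allocated 1:1, so about 20 per arm (9.1, 8.5); about 5% loss (6.4.3), so 40 × 0.95 = 38, or 19 per arm. For an unadjusted difference in SD units, SE = √(2/n):

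- n = 20: √(2/20) = 0.316; 95% half-width 1.96 × 0.316 = 0.62.
- n = 19: √(2/19) = 0.324; 95% half-width 1.96 × 0.324 = 0.64.

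As an assumption only, take mE − mW between 0.1 and 0.3 SD. At 20 per arm that is 0.1/0.316 = 0.32 to 0.3/0.316 = 0.95 standard errors. A shift in that range could not be told apart from chance or from a real effect. The range is illustrative; no value can be derived from the documents.

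**The case against.** The strongest reply is that this is a feasibility pilot. Its primary endpoint is adherence (4.1.1), and section 2.1 warns that small samples misjudge effect sizes. At 20 per arm the 95% half-width of 0.62 SD is about 2 to 6 times the assumed bias (0.62/0.3 = 2.1; 0.62/0.1 = 6.2). Women cannot be masked to exercise, so part of any effort effect would remain whatever is done. All of this stands, and it limits the point to a cheap improvement in secondary results. It does not remove the point: between-group functional differences are still planned, and chance error does not excuse an avoidable systematic one.

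Several stronger readings are tempting, but the documents do not support them:

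- **That the functional estimate will set the next trial's sample size.** Section 9.3.1 speaks only of gauging how large changes might be, and section 2.1 gives the purpose as testing logistics for a future design. Any loss of power in a later trial would be speculation.
- **That the coaching coordinator is the tester.** It is a fair possibility, but 8.4.4 names nobody and 10.3 refers to data-collection personnel in general.
- **That testing is unstandardised.** Sections 8.1 and 10.3 provide procedures and training. What is missing is encouragement wording and assessor independence. The supplied appendices stop at Appendix 3, although 6.4.2 cites an Appendix 7, so a script in material not seen cannot be ruled out.
- **That only the exercise arm has rapport with the coordinator.** Sections 10.4 and 11 say both groups receive check-in calls, whereas section 8 and Appendix 1 place the coaching calls in the exercise arm. Appendix 1 also lists the interview under assessments for all participants, while section 8 limits it to the exercise arm. Even with equal contact, the wait-list session would still disclose the arm.

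Appendix 1 already has a staff-initials column, so part of the record of who tested may exist.

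**Conclusion.** The point holds for secondary and exploratory results. The arm is known at the final visit, four of the six fitness tests depend on effort, and the supplied text does not separate testing from knowledge of the arm. The between-group functional differences could be biased, probably in favour of exercise. That direction is a judgement, resting on the coaching relationship and the expectation that training helps.

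The size of the bias is unknown. The 0.1 to 0.3 SD range is assumed, and the standard error of 0.32 SD rests on 20 women per arm and an unadjusted comparison. The adherence endpoint and retention do not depend on these tests and are unaffected.

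**What to change.** In 8.4.1 and 8.4.4:

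1. Use the same written instructions and encouragement wording for each fitness test, at both visits and in both arms.
2. Complete all physical measures before the wait-list session or the exit interview.
3. Analyse baseline and final DXA scans by study ID with the arm withheld.
4. Where an existing trained team member who did not coach the woman is available, have that person score her final tests on a sheet that does not show the arm.

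In 9.3.1, state that functional outcomes were otherwise assessed unmasked and that their between-group estimates should be read with that limit.

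The cost is protocol wording, a short test script and slightly less scheduling flexibility at the final visit. No extra staff, visits or participants are needed. Item 4 may seldom be possible in a team with one main coordinator; the other items and the statement in 9.3.1 do not depend on it.
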